- h A serum pregnancy test will be performed at the Screen A visit for WOCBP or at any point in time if a pregnancy is suspected. All other pregnancy assessments will be urine pregnancy tests. Additional pregnancy assessments will be performed more frequently if required by local law or requested by local regulatory authorities or IRBs/ECs.
- i AE assessments on Day 1 should be performed following study drug administration.
- j Kidney ultrasound (historical or one obtained during screening) may be used to diagnose ADPKD for patients without a prior ADPKD diagnosis.
- k eGFR will be calculated and appear on lab reports for Screen A and Screen B visits, eGFR will no longer be calculated for any visits after the Screening period.
- l Albumin to creatinine ratio will be measured by first morning void spot urine collection. Appropriate containers for the collection will be provided to the patient at the visit prior to collection.
- m ██████████  
██████████
- n Patients must refrain from taking study drug prior to coming to the clinic for PK draws at Week 12 and Week 100.
- o Ambulatory Blood Pressure Monitoring (ABPM) is an optional sub-study for adult patients ( $18 \leq \text{age} \leq 70$  years at Screen A) who enroll under protocol version 6.0 (or greater) and consent to the procedure prior to randomization. See Section 9.10.33 for details and timing on ABPM. ABPM will not be performed on adolescent patients ( $12 \leq \text{age} < 18$  years at randomization)
- p For patients who consent to the optional ABPM sub-study, the initial (baseline) 24-hour monitoring assessment must be done during the Screening period prior to Day 1. See Section 9.10.33 for detailed information.
- q Adolescent patients ( $12 \leq \text{age} < 18$  years at Screen A visit) will be assessed by Tanner staging at all specified timepoints.
- r For adult patients who consent to the optional ABPM sub-study, the final 24-hour monitoring assessment occurs after Week 88 and prior to Week 100 (last dose). For patients who discontinue study drug prior to Week 100, patients who consented to ABPM should have the assessment at End of Treatment if no ABPM was conducted in the four weeks prior to the date of last dose.
- s See Section 8.3.3 and Section 8.5.1 for details on the Off-Treatment Period.

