### **9.10.33. Ambulatory Blood Pressure Monitoring**

For adult patients, Ambulatory Blood Pressure Monitoring (ABPM) is an optional sub-study conducted at the timepoints specified in Table 4. To participate, patients must have a baseline ABPM assessment. The baseline assessment must occur during the screening period, ideally 2-3 days prior to Day 1. The additional assessments occur at the following time points: Week 12, Week 48, and between Weeks 88 and 100 (prior to the patient's last dose of study drug), as defined in [Table 4](#).

Participation in the ABPM sub-study is optional; however, patients should be encouraged to participate, and use of home health visits is strongly encouraged to minimize the burden on the patient and to maximize participation.

To ensure a sufficient volume of ABPM data, the Sponsor may halt enrollment of patients not participating in the ABPM sub-study. Participation will be monitored closely as overall enrollment progresses, and the Sponsor will update sites on progress toward achieving sufficient ABPM participation.

A Sponsor-provided device will be placed on the patient by the study team, and the patient must wear the device for approximately 24 hours.

Upon completion of the 24-hour period, the site will collect the device from the patient and ABPM data will be sent to the central vendor to determine if the 24-hour recording passes the validity criteria. The criteria used to define a valid ABPM session for sites to determine the need for a repeat 24-hour session, if possible, are:

- At least 70% of planned inflations are successful during the overall recording session;
- At least 18 hours of analyzable data, and;
- Not more than two consecutive hours of missing data.

For detailed instructions regarding ABPM refer to the study reference manual.

The addition of ABPM to the schedule of assessments occurred through a protocol amendment, and site and patient participation will be offered, once available.

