6.5.2. Visit Windows

Analysis visits and their windows are defined using derived study day (Section 6.5.1) instead of relying on visit labels in the clinical database because clinical visits may occur outside protocol-specified windows. Study day and days after last dose are calculated using the actual date of each scheduled and unscheduled assessment and compared to the target for each analysis visit as specified in Table 4 and Table 5. They are included in analyses of safety and efficacy as follows:

- Efficacy analyses for endpoints assessed through Week 100 use the analysis windows in Table 4, irrespective of whether or not a patient is receiving treatment of study drug.
- Efficacy analyses for endpoints assessed during the follow-up period after Week 100 use the analysis window in Table 4 irrespective of how long a patient has been off-treatment.
- Protocol version 6 eliminated the off-treatment period from Week 48 to Week 52. Patients completing the Week 52 visit prior to consenting to protocol version 6 will be considered “off-treatment” at Week 52. All other patients are expected to be on-treatment at Week 52. Week 52 analysis values in Table 4 will not be used in the efficacy analyses unless otherwise specified. Week 52 values are only summarized descriptively because of the mix of on-treatment and off-treatment values.
- Safety analyses use the analysis windows defined in Table 4 so long as the patient is receiving treatment of study drug. Once a patient permanently discontinues study treatment, safety data are summarized according to time since last dose as defined in Table 5.

Unless otherwise specified if a parameter is assessed or measured more than once within a visit window, the one that is closest to the protocol-scheduled time point (i.e., target) is used for the purposes of data analysis and summary.

If 2 assessments are equidistant from a target, the earlier assessment is used. If 2 assessments are on the same day, the average of 2 assessments will be used for non-laboratory parameters. For laboratory parameters, if both an original and retest result are available in the laboratory dataset, the original result will be used and the second (i.e., “retested”) result will be ignored.

One exception is that 2 scheduled chemistry values (including eGFR) are collected within the Week 52 (prior to protocol version 6), Week 104, Week 108, and Week 112 analysis windows.

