9.7. Vital Signs

Vital signs assessments include systolic blood pressure (SBP, mmHg) and diastolic blood pressure (DBP, mmHg), body temperature (°C), heart rate (HR, bpm), height (cm), weight (kg), and BMI (kg/m²). Vital signs are summarized at baseline and at each time point along with the change from baseline by treatment. Boxplots and line graphs of change from baseline over time for blood pressure are plotted.

In addition, a summary table is provided for the number and percentage of patients meeting a following pre-specified post baseline on-treatment blood pressure change categories:

- SBP (mm Hg):
 - Maximum increase from baseline: ≥ 20 ; ≥ 40 ; ≥ 60
 - Maximum decrease from baseline: ≥ 20 ; ≥ 40
- DBP (mm Hg):
 - Maximum increase from baseline: ≥ 20 ; ≥ 40
 - Maximum decrease from baseline: ≥ 20

9.8. 24-hr ABPM Sub-study

A subset of patients who consent to the 24-hour ambulatory blood pressure monitoring (ABPM) sub-study will have systolic blood pressure, diastolic blood pressure, pulse pressure and heart rate collected during 24-hour periods as specified in [Table 2](#). Observed values and change from baseline will be summarized at baseline and at analysis visits Week 12, Week 48 and Week 88 for each 24-hour ABPM assessment using the following 24-hour parameters: overall mean, daytime mean, and nighttime mean. Descriptive summaries will include confidence intervals.

The 24-hour ABPM parameters will be calculated as specified in [Table 11](#). For each 24-hour period, calculation of the average values is the sum of all valid ambulatory blood pressure measurements divided by the number of all valid blood pressure measurements, within the range of time specified for the parameter. Categorical summaries for systolic blood pressure and diastolic blood pressure described in [Section 9.7](#) will also be performed.

Table 11: 24-HOUR ABPM PARAMETERS

Parameter	Calculation
Overall (24-hour) SBP, DBP mean	average of all valid measurements taken from the patient’s ambulatory blood pressure monitoring device
Daytime SBP, DBP mean	average of all valid measurements taken from 6 am to 10 pm
Nighttime SBP, DBP mean	average of all valid measurements taken from 10 pm to 6 am next day

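### SAP 9.8 sets no session-level validity rule for ambulatory blood pressure recordings, so at Weeks 12 and 48 the closest-to-target rule can keep a failed session and drop its valid repeat

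*SAP*

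**What the plan says.** Protocol 9.10.33 has the central vendor check each recording against three criteria. The first is a success rate: "At least 70% of planned inflations are successful during the overall recording session". The second is a duration: "At least 18 hours of analyzable data". The third is a limit on gaps: "Not more than two consecutive hours of missing data". It introduces them as "The criteria used to define a valid ABPM session for sites to determine the need for a repeat 24-hour session, if possible". It does not make them a condition for entering an analysis.

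SAP 9.8 summarises ABPM at baseline and Weeks 12, 48 and 88. Its formula reads: "calculation of the average values is the sum of all valid ambulatory blood pressure measurements divided by the number of all valid blood pressure measurements". The formula is applied to each recording separately and only to readings in the clock hours of the parameter. Table 11 defines an overall mean over all valid readings, a daytime mean (6 am to 10 pm) and a nighttime mean (10 pm to 6 am). Validity here belongs to the reading, and the SAP does not define it. Neither 9.8 nor Table 11 cites the session criteria or sets a minimum number of hours, a success rate or a gap limit.

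For several records in one window, SAP 6.5.2 says "the one that is closest to the protocol-scheduled time point (i.e., target) is used", and the earlier record wins a tie. SAP Section 6 leaves repeats that are not nearest to target out of the summary tables unless another section says otherwise. SAP 9.8 does not say otherwise.

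**The concern.** The protocol asks sites to obtain a repeat because the first recording was inadequate. The SAP's selection rule looks only at distance from the target day. Because a repeat comes after the failure it replaces, the rule tends to keep the failed recording and discard the good one.

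With no session-level requirement, a failed recording can still produce an overall 24-hour mean. If the missing hours are mostly at night, that figure is close to a daytime mean. The error passes into the change from baseline, its confidence interval, and the categorical tables of maximum systolic and diastolic change that SAP 9.8 takes over from 9.7. The SAP governs where it differs from the protocol, so its silence leaves the choice to whoever programs the tables.

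**Working it through.** **Selection rule.** Inputs from SAP Table 4: Week 12 has target Day 84 and window Days 71 to 126; Week 48 has target Day 336 and window Days 295 to 350. Rule: take the smallest |study day − target|, ties to the earlier record.

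| Visit | Failed session | Valid repeat | Distances | Record used |
|---|---|---|---|---|
| Week 12 | Day 84 | Day 91 | 0 vs 7 | Day 84 (failed) |
| Week 12 | Day 81 | Day 87 | 3 vs 3 | Day 81 (failed, by the tie rule) |
| Week 12 | Day 80 | Day 86 | 4 vs 2 | Day 86 (repeat) |
| Week 48 | Day 336 | Day 343 | 0 vs 7 | Day 336 (failed) |

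A first attempt on or after the target day always beats a later repeat. An earlier attempt loses only if the repeat is strictly nearer.

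To see how often this happens, assume the first attempt is within 3 days of target (the protocol visit window) and the repeat comes 1 to 14 days later. The 14-day span is my assumption.

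- Week 12: 7 first days × 14 delays = 98 combinations. The repeat wins in 5 when the first attempt is 3 days early, 3 when 2 days early and 1 when 1 day early, 9 in all. The failed session is used in 98 − 9 = 89.
- Week 48: 6 of the 98 combinations put the repeat after Day 350, outside the window, leaving 92. The repeat again wins in 9, so the failed session is used in 83.

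These count calendar combinations. They are not estimates of how many patients are affected.

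**Size of the distortion.** The SAP's daytime window is 16 hours and its nighttime window 8. Let D be the daytime mean minus the nighttime mean, and assume evenly spaced readings. The documents give neither.

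- Full-day mean = (16 × day + 8 × night)/24 = day − D/3.
- A 16-hour daytime-only recording fails the 18-hour criterion and returns the daytime mean, so the overall mean is too high by D/3.
- A recording with 16 day hours and 2 scattered night hours can pass: 18 hours, 18/24 = 75% of inflations, and the 6 missing hours split into gaps of 2. Its shift is (8/24 − 2/18) × D = 0.22 × D.

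| Assumed D (mmHg) | Daytime only (fails) | 16 h day + 2 h night (just passes) |
|---|---|---|
| 5 | 1.7 | 1.1 |
| 10 | 3.3 | 2.2 |
| 15 | 5.0 | 3.3 |
| 20 | 6.7 | 4.4 |

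The session criteria limit this error without removing it.

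**Baseline.** Closest-to-target does not apply there. SAP 6.4 takes the last pre-dose value, which would favour a repeat. SAP 6.4.4 averages pre-dose values for vital signs and other continuous safety measures, which would mix a failed session with its repeat. The SAP does not say which covers ABPM.

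**The case against.** The strongest reply is that the SAP contradicts nothing. The protocol offers the criteria for the site's decision to repeat, and the SAP does not say that failed sessions are analysed. The vendor may not transfer them, and the protocol leaves further ABPM detail to a study reference manual that is not among the documents. This stands, so the point is an unspecified session-level rule and not a conflict between documents. It does not rescue the selection rule, which is written down and, if both recordings reach the database, often drops the one the protocol asked for.

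A reader might infer that the problem is worst at the final recording: it is taken after Week 88, so any later repeat in the window is further from Day 616. That follows from the rule but is empty here. Protocol Table 4 limits ABPM to patients enrolled under version 6.0 or later, dated 4 February 2022, and SAP Section 2 puts the termination notice at 10 May 2023. A patient first dosed on 4 February 2022 would then be at Day 461. Likewise, reaching Day 336 by the notice requires a first dose by about 9 June 2022, so Week 12 is the main live case.

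A reader might also infer a bias between arms. The documents give no reason to expect more failed sessions in one arm, and no failure rate at all. The separate daytime and nighttime means are not exposed to day-night mixing.

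**Conclusion.** The point holds in a limited form. SAP 9.8 and Table 11 apply no session-level validity filter, and SAP Section 6 with 6.5.2 selects records without regard to validity. At Weeks 12 and 48 a failed session is used instead of its valid repeat whenever it is nearer to target or tied with it. It is not used in every case.

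The distortion of an affected overall mean is one third of the day-night difference for a daytime-only recording. Any mmHg figure rests on an assumed difference and evenly spaced readings, and the number of affected records cannot be derived from the documents. The sub-study is optional, its summaries are descriptive, and the eGFR endpoints are untouched. Severity is low.

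**What to change.** State in SAP 9.8, as an exception to Sections 6 and 6.5.2:

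1. Where a session meeting the three Protocol 9.10.33 criteria exists in the visit window, it is used in preference to a failed one. Closest-to-target applies only among passing sessions.
2. The same preference applies at baseline.
3. Overall 24-hour means are summarised only from passing sessions.
4. Failed sessions are listed.

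The cost is a few sentences and minor programming, since the vendor already determines whether each recording passes. The downside is that a patient with only a failed session drops out of that visit's 24-hour summary. Reweighting the overall mean to fixed day and night shares is not needed: it is undefined without night readings and gives a few sparse ones a full third of the weight.

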9.9. Electrocardiogram

Electrocardiogram (ECG) data, such as clinical interpretation of ECGs, heart rate and interval assessments of PR, QRS, and QT are collected on the eCRF. QTcF is calculated for analysis (Section 6.5.6). Descriptive statistics for observed values and change from baseline at each time point are presented for these 12-lead ECG interval assessments. In addition, number and percentage of patients with any abnormal values (i.e., above a pre-specified threshold) at any time during the study are summarized by time point and overall. The pre-specified levels of ECG QTcF thresholds (Table 12) are consistent with FDA guidance:

Table 12: PRE-SPECIFIED THRESHOLD LEVELS FOR ECG PARAMETERS

ECG Parameter	Pre-Specified Level
PR	>200 msec
QTcF	>450 and ≤480 msec
	>480 and ≤500 msec
	>500
	Change from baseline: >30 and ≤60 msec
	Change from baseline: >60 msec
Heart rate	<40 beats/min
	>100 beats/min

Line graphs of change from baseline over time for ECG parameters are plotted.

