9.5.2. Categorical Summaries of Laboratory Results

Select laboratory parameters will be summarized using shift tables. Shift tables are summarized by treatment, laboratory category (hematology, chemistry, urinalysis, and microscopy), and laboratory test and present shifts from baseline status (Normal, Low, High) to worst on study treatment status (Normal, Low, High). The worst abnormality values are defined as the maximum values while on study treatment (i.e., up to <21 days after last dose), with the exception of magnesium and hemoglobin. The worst abnormal values for magnesium and hemoglobin are defined as the minimum values while on study treatment (i.e., up to <21 days after last dose).

Additionally, laboratory parameters of specific interest (ALT, AST, ACR, BNP) are summarized using shift tables that summarize shifts from (1) baseline status to end of treatment status, (2) worst on-treatment status to worst off-treatment status, (3) worst on-treatment status to end of study, and (4) baseline status to worst on-treatment status 5) baseline to worst off-treatment, and (6) worst on-treatment status to best (lowest) off-treatment status. The number and percentage of patients are summarized. For ACR, summaries will present shifts from/to the categories listed in Section 6.5.5.1. For ALT and AST, summaries will present shifts from/to the following categories:

- \leq ULN
- $>$ ULN to $<3 \times$ ULN
- $\geq 3 \times$ ULN to $<5 \times$ ULN
- $\geq 5 \times$ ULN to $<10 \times$ ULN
- $\geq 10 \times$ ULN to $<20 \times$ ULN
- $\geq 20 \times$ ULN

For BNP, summaries will present shifts from/to the following categories:

- <100 pg/mL
- ≥ 100 pg/ml to <200 pg/ml
- ≥ 200 pg/ml to <400 pg/ml
- ≥ 400 pg/ml

In addition, a summary table is provided for the number and percentage of patients meeting a following pre-specified threshold level at any time during the study:

- ACR >3500 mg/g
- Magnesium <1.3 mEq/L (0.65 mmol/L)
- BNP >200 pg/mL
- NT-proBNP >1000 pg/mL

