9.5.2.1. Transaminases

Evaluation of Drug-Induced Serious Hepatotoxicity (eDISH) plots are generated for ALT and AST versus TBL.

The number and percentage of patients meeting the following thresholds (Table 10) at any time during the study are summarized by the maximum dosage received. The pre-specified thresholds are consistent with FDA guidance.

Table 10: PRE-SPECIFIED THRESHOLD LEVELS FOR TRANSAMINASES

Lab Parameter	Threshold
ALT, AST	$\geq 3 \times$ upper limit of normal (ULN) and $<5 \times$ ULN

Lab Parameter	Threshold
	$\geq 5 \times \text{ULN}$ and $< 10 \times \text{ULN}$
	$\geq 10 \times \text{ULN}$ and $< 20 \times \text{ULN}$
	$\geq 20 \times \text{ULN}$
	$\geq 5 \times \text{ULN}$ for more than 2 weeks
TBL	$\geq \text{ULN}$ and $\leq 1.5 \times \text{ULN}$
	$> 1.5 \times \text{ULN}$ and $\leq 2 \times \text{ULN}$
	$> 2 \times \text{ULN}$
ALT, AST, TBL	ALT or AST $> 3 \times \text{ULN}$ and TBL $> 1.5 \times \text{ULN}$
	ALT or AST $> 3 \times \text{ULN}$ and TBL $> 2 \times \text{ULN}$
ALT, AST, TBL, International normalized ratio (INR)	$> 3 \times \text{ULN}$ and (TBL $> 2 \times \text{ULN}$ or INR > 1.5)
ALP	$> 1.5 \times \text{ULN}$

A listing of subjects with abnormal ALT, AST, or TBL will also be provided.

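### Several laboratory, liver and ECG threshold counts have no on-treatment limit, so off-drug values (and for some parameters pre-dose values) can count as events.

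*SAP*

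**What the plan says.** Section 9.9 counts patients with "any abnormal values (i.e., above a pre-specified threshold) at any time during the study" against the limits in Table 12, and says the counts "are summarized by time point and overall". Section 9.5.2 counts patients "meeting a following pre-specified threshold level at any time during the study" for ACR above 3500 mg/g, magnesium below 1.3 mEq/L, BNP above 200 pg/mL and NT-proBNP above 1000 pg/mL. In Section 9.5.2.1, patients meeting a Table 10 threshold "at any time during the study are summarized by the maximum dosage received". Table 10 covers ALT, AST, total bilirubin (TBL) and ALP, together with rows that combine ALT or AST with TBL or INR.

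Elsewhere the SAP does limit the period. Section 9.7 tabulates patients "meeting a following pre-specified post baseline on-treatment blood pressure change categories". In the shift tables of Section 9.5.2 the worst values are the "maximum values while on study treatment (i.e., up to <21 days after last dose", with the minimum taken for magnesium and hemoglobin. Section 6.5.2.1 treats assessments through 20 days after the last dose as on-treatment and groups later ones in Table 5.

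**The concern.** A threshold table in a safety section is normally read as a count of what happened on drug. If off-drug values also count, background exceedances enter both arms and pull the drug-to-placebo ratio toward 1.

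Table 10 has a further difficulty. Its counts are grouped by the maximum dose received, so a value taken long after stopping is attributed to a dose. It also sets no time link between the ALT/AST value and the TBL or INR value in the paired rows, so an on-drug ALT rise and an unrelated bilirubin value months later could together make a case. Protocol Section 5.1.2.2 reports ALT/AST above 3x ULN in about 4% to 11% of treated patients, without accompanying bilirubin elevation, so an unlinked pair could give a false signal of liver injury. Finally, bands counted over the whole study can place one patient in several rows, so they cannot be added up to a total at or above 3x ULN.

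**Working it through.** The plan states no figure for these tables, so there is nothing to reproduce. The check compares the stated periods and then sizes the effect.

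**1. Off-drug follow-up that could count.**
- Completers: the last ECG is Week 108B, 57 to 64 days after last dose (about 8 weeks). The last chemistry is Week 112B, 85 to 92 days (about 12 weeks). Of the six scheduled ECGs (Screen A, Weeks 48, 52, 100, 104B, 108B), at most three are on drug.
- Early stoppers: Protocol Section 8.3.3 continues assessments through Week 112. The last Table 5 window ends at 686 days: 686/7 = 98 weeks, 686/365.25 = 1.9 years. At the extreme, stopping on Day 1 with a last visit on Day 792 gives 791 days, or 113 weeks (2.2 years).

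**2. Which rows have an on-treatment counterpart.**

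| Row | On-treatment version elsewhere in the SAP |
|---|---|
| ALT/AST bands at 3, 5, 10, 20 x ULN | Yes: baseline-to-worst-on-treatment shift, same cut-points (9.5.2) |
| BNP >200 pg/mL | Yes: shift categories cut at 200 (9.5.2) |
| ACR >3500 mg/g | No: shifts use only the 300 mg/g cut (6.5.5.1) |
| Magnesium <1.3 mEq/L | At most a Normal/Low/High shift, if selected |
| Graded TBL; ALP >1.5x ULN | At most a Normal/Low/High shift, if selected |
| NT-proBNP >1000 pg/mL | No version at that cut-point |
| ALT/AST >=5x ULN for more than 2 weeks | None |
| Paired ALT/AST with TBL or INR | None |
| ECG, overall row | None; counts by time point only |

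**3. Pre-dose values.** Eligibility requires ALT, AST and TBL at or below ULN and BNP not above 200 pg/mL at Screen A, and ACR at or below 2500 mg/g at Screen B. Pre-dose exceedances are therefore largely ruled out for those parameters, and the QTcF change-from-baseline rows cannot be met pre-dose. PR, absolute QTcF, heart rate, magnesium, NT-proBNP and ALP have no numerical entry limit, so a pre-dose exceedance could count.

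**4. Size, in general.** Let p be the on-treatment rate in an arm and q the rate of an off-drug or pre-dose exceedance, assumed equal in both arms and independent of p. The pooled rate is P = 1 - (1 - p)(1 - q), so the risk difference is multiplied by (1 - q). Take p = 4% on drug (the low end of the protocol's range, used only for scale) and an assumed 1% on placebo. Power is a gauge of precision only, at 425 per arm.

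| q | Drug | Placebo | Difference (points) | Ratio | Power |
|---|---|---|---|---|---|
| 0 | 4.00% | 1.00% | 3.00 | 4.00 | 80% |
| 1% | 4.96% | 1.99% | 2.97 | 2.49 | 66% |
| 2% | 5.92% | 2.98% | 2.94 | 1.99 | 55% |
| 5% | 8.80% | 5.95% | 2.85 | 1.48 | 36% |
| 10% | 13.60% | 10.90% | 2.70 | 1.25 | 22% |

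With 11% against 1%, the ratio falls from 11 to 6.0, 4.3, 2.6 and 1.8 over the same non-zero values of q, and power stays at or above 95%.

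**5. Size, ECG overall row.** Assume an abnormality risk per ECG of 2% off drug and 4% on drug, with independent readings.
- Three on-drug ECGs only: placebo 1 - 0.98^3 = 5.9%; drug 1 - 0.96^3 = 11.5%. Ratio 1.96, difference 5.6 points.
- All six ECGs: placebo 1 - 0.98^6 = 11.4%; drug 1 - (0.98^3)(0.96^3) = 16.7%. Ratio 1.47, difference 5.3 points.

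Repeat ECGs in one patient are correlated, so this shows the direction of the effect and is not a forecast.

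**The case against.** The strongest reply is that Sections 6.5.2, 6.5.2.1 and 9 already separate on-treatment from off-treatment safety data, and the threshold sections do not claim to override that. It has some force: the authors may have intended the split to apply here. But the SAP does not say so, and the wording of the three sections points the other way.

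A reader might infer that the on-drug signal is lost across all three tables and that screening values count throughout. The documents do not support that. ECG counts also appear by time point. Eligibility limits largely exclude pre-dose exceedances for ALT, AST, TBL, BNP and ACR. The shift tables give each patient's worst on-treatment ALT and AST at the Table 10 cut-points, so the number at or above 3x ULN on drug can be obtained for each test. No on-drug event is dropped, and the risk difference barely moves.

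Two qualifications remain. Counts by visit do not give the number of patients with any on-drug ECG abnormality, and Week 52 itself mixes on- and off-drug patients because of the withdrawal period used before protocol version 6 (SAP 6.5.2). For the paired rows, the planned eDISH plots and the listing of abnormal ALT, AST or TBL would help a reader notice a mismatched pair, but the tabulated count would still include it.

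It is also fair to say that these are descriptive tables, that Section 9 plans no safety testing unless otherwise specified, and that the SAP records that clinical development has been discontinued.

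**Conclusion.** The point holds for a defined set of rows: the overall ECG row, graded TBL, the paired ALT/AST-TBL-INR rows, ALT/AST >=5x ULN for more than 2 weeks, ALP, NT-proBNP >1000 pg/mL, magnesium <1.3 mEq/L and ACR >3500 mg/g. For these the SAP counts over the whole study and specifies no on-treatment version at the same cut-point. The period rule is inconsistent with the SAP's own treatment of blood pressure and of worst laboratory values.

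The cost is in ratios and precision; risk differences lose only a factor of (1 - q). All the rates used for sizing are assumptions except the protocol's 4% to 11%, and the true off-drug and pre-dose rates are not in the documents. The figure of about two years applies to early stoppers only. It would be wrong to read this as an ECG or transaminase signal being hidden, for the reasons given above.

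**What to change.** Define the counts in Sections 9.5.2 and 9.5.2.1 and the overall row of Section 9.9 as post-baseline and on-treatment, using the existing rule of through 20 days after last dose (Section 6.5.2.1). Show off-treatment counts in a separate column.

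For the paired rows, require the TBL or INR value to fall within a pre-specified time window of the ALT/AST elevation. Thirty days is one option; it does not come from the documents.

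For the ALT/AST bands, count each patient once at the worst band, or replace the bands with cumulative thresholds (>=3, >=5, >=10 and >=20 x ULN).

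The cost is SAP wording and one extra column per table, using a period the SAP already defines. No efficacy result changes.
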